4.5 Women of childbearing potential

4.5.1 Definition of childbearing potential

A woman is considered to be of childbearing potential unless she meets at least one of the following criteria:

- Previous bilateral salpingectomy, bilateral salpingo-oophorectomy or hysterectomy.
- Premature ovarian failure confirmed by a specialist.
- XY genotype, Turner syndrome, uterine agenesis.
- Post-menopausal, defined as 12 consecutive months with no menses without an alternative medical cause (ICH M3 definition).

4.5.2 Acceptable methods of contraception

WOCBP [definition see Section 4.5.1] must follow the below contraception scheme up to at least 30 days after study treatment discontinuation:

- Two methods of contraception, one from Group 1 and one from Group 2, defined as follows:
 - Group 1: Oral, implantable, transdermal or injectable hormonal contraceptives, which are associated with inhibition of ovulation, or intrauterine devices. Methods of contraception from Group 1 must be taken for at least 30 days prior to randomization.
 - Group 2: Female or male condoms, diaphragm or cervical cap.

OR

- True abstinence from intercourse with a male partner only when this is in line with the preferred lifestyle of the subject. If true abstinence from intercourse with a male partner is chosen, then it must be started at latest at Visit 1 (Screening).
OR
- Permanent female sterilization (tubal occlusion/ligation at least 6 weeks prior to Visit 1 (Screening)).
OR
- Sterilization of the male partner with documented post-vasectomy confirmation (prior to randomization) of the absence of sperm in the ejaculate.

Rhythm methods or the use of a condom by a male partner alone are not considered acceptable methods of contraception for this study.

The methods of contraception used (including non-pharmacological methods) must be recorded in the eCRF.

4.6 Medical history

4.6.1 General Medical History

Relevant medical history, as defined below, must be recorded in the eCRF:

- Significant chronic medical conditions at any time prior to the study (in the opinion of the investigator);
- Significant (in the opinion of the investigator) cardiovascular, pulmonary, liver, renal, eye disorder, and skin conditions, serious infections leading to hospitalization, and malignant tumors at any time prior to the study;
- Medically significant new acute medical conditions in the past 12 months prior to the study (in the opinion of the investigator);
- Smoking status at the time of entry in the study;
- Episodes of anaphylaxis, angioedema, flushing in the past 12 months.

Previous and concomitant therapies at pre-randomization, as defined in Section 5.2, will be recorded in the previous/concomitant medication page of the eCRF.

4.6.2 MS history

MS disease characteristics, as defined below and evidenced by documentation in the patient charts, will be recorded on the MS history page of the eCRF:

- Date of first known MS symptoms;
- Date of MS diagnosis;
- MS type (e.g., RRMS, SPMS);

- Symptoms associated with MS (e.g., optic neuritis, numbness, spasticity, tremor, fatigue, dizziness, dysfunctional bladder, cognitive problems, etc.) within the last 24 months prior to the study;
- Number of documented MS relapses within the last 12 months and between 12 and 24 months prior to the study. The onset date and the duration of the relapse when available, and treatment of these relapses (corticosteroids, ACTH, plasmapheresis etc.) will be reported;
- Number of documented Gd+ lesions per scan and number of documented T2 hyperintense lesions per scan on any MRI scan performed within 24 months prior to the study. Additionally, the condition of the MRI scan will be collected (e.g., scanner type, manufacturer and strength, the type of T1 sequence and number of slices used to detect Gd+, contrast agent used [Gd type], dose of contrast agent and time of injection, time of T1 sequence, the type of T2 sequence and number of slices used to detect T2 hyperintense lesions);
- Previous MS disease-modifying treatments received at any time in the past. For treatments received in the last 24 months prior to the study, start date, end date, dose, route, frequency, and reason for discontinuation will be recorded in the previous/concomitant medication page of the eCRF [see Section 5.2.2].

5 TREATMENTS

5.1 Study treatment

The treatment period consists of an up-titration period (from Day 1 to 14) and a maintenance period (Day 15 until EOT).

In the maintenance period, the study treatment consists of the daily administration of one tablet containing ponesimod 20 mg [see Section 5.1.8] (or matching placebo).

5.1.1 Investigational treatment and matching placebo: description and rationale

Ponesimod is supplied as its free base, in oral film-coated tablets at the doses of 2, 3, 4, 5, 6, 7, 8, 9, 10, and 20 mg.

During the up-titration period (Day 1 to 14) and the maintenance period, one tablet of ponesimod 2, 3, 4, 5, 6, 7, 8, 9, 10, or 20 mg (or matching placebo) will be taken orally o.d. The matching placebos for the doses of 2, 3, 4, 5, 6, 7, 8, 9, 10, and 20 mg are supplied as identical tablets, formulated with the same excipients but without the active ingredient, ponesimod. The 20 mg tablets and their matching placebo dispensed during the treatment maintenance are identical and indistinguishable and will be packaged in the same way.

The proposed add-on design will assess the superiority of ponesimod over placebo on a background of DMF therapy, an approved disease modifying therapy for the treatment of

RMS. The use of a placebo comparator is additionally justified by the provision of the option to switch to an alternative treatment or to remain on study treatment for subjects who meet at least one of the following conditions:

- Subjects have experienced a confirmed relapse;
- Subjects have experienced an event of 24-week CDA.

In any of the above cases, the subject will be asked to re-consent to continue receiving study treatment [see Section 13.3].

5.1.2 Study treatment administration

One tablet of ponesimod (or matching placebo) will be taken orally o.d. During the titration, the tablet will be taken in the morning, either with breakfast or before or after breakfast. During maintenance, the tablet will preferably be taken in the morning (either with breakfast or before or after breakfast). Overall, it is preferable that the tablet is taken each day at approximately the same time. The tablet will be swallowed as a whole. The last administration date and time of study treatment prior to the study visits and the administration date and time of study treatment on the days of visits will be recorded in the eCRF.

5.1.2.1 Titration

A gradual up-titration of ponesimod from a 2 mg starting dose to a 20 mg maintenance dose over a period of 14 days was found to successfully mitigate first-dose effects on HR and AV conduction. This 2-week up-titration regimen will be implemented in the study on initiation of treatment (Day 1) and on days of re-initiation of treatment following treatment interruption of more than 3 days [see Section 5.1.9].

Table 4 Dosing scheme

Treatment period	Duration	Dose regimen in the ponesimod group
Titration	Day 1 and 2	2 mg
Titration	Day 3 and 4	3 mg
Titration	Day 5 and 6	4 mg
Titration	Day 7	5 mg
Titration	Day 8	6 mg
Titration	Day 9	7 mg
Titration	Day 10	8 mg
Titration	Day 11	9 mg
Titration	Day 12 to 14*	10 mg
Maintenance	Day 15 until EOT	20 mg

* Visit 4 is to take place at Day 15 ± 1 day.

EOT = End-of-Treatment; NA = not applicable.

Study treatment up-titration, other than described above, is prohibited. Study treatment down-titration is not foreseen in any situation and is prohibited.

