5.1.8 Study treatment dose adjustments and interruptions

Study treatment up-titration, other than described in Section 5.1.2.1, is prohibited. Study treatment down-titration is not foreseen in any situation and is prohibited.

Study treatment interruption should be avoided. If study treatment intake is interrupted by the subject for any reason, she/he must immediately inform the investigator / treating neurologist.

Study treatment may be temporarily interrupted (i.e., re-start of the study treatment is possible) in response to an AE, a diagnostic or therapeutic procedure, a laboratory abnormality, or for administrative reasons. Study-specific criteria for interruption of study treatment are described in Section 5.1.12. The duration of a temporary interruption is determined by the investigator and is not limited in time. At maximum, it will last until the investigator deems necessary to require another MS treatment for the subject, which would end the temporary interruption and trigger permanent discontinuation of the study treatment.

Detailed guidance on how to re-initiate study treatment in the event of drug interruption is provided in Section 5.1.9.

Study treatment dose adjustments/interruptions must be recorded in the eCRF.

5.1.9 Guidance for re-initiation of study treatment in the event of study treatment interruption

If study drug intake is interrupted by the subject for any reason, she/he must immediately inform the principal investigator / treating neurologist.

The following guidance is provided for re-initiation of investigational study drug after study drug interruptions.

A schematic overview of the re-initiation algorithm is given in [Figure 2](#).

Depending on the day, time, and duration of study drug interruption, the following procedures will be followed.

[figure not shown]
- If the subject missed taking the dose in the morning:
 - The dose should be taken at any time on the same day.
 - Regular dosing should be resumed with the morning dose on the following day.
- If the subject missed taking the dose for one or more days during treatment up-titration (from 1 to 14 days after the first-dose of initiation/re-initiation of the study drug):
 - The original up-titration scheme needs to be re-applied, with the initial dose and gradual up-titration steps for 14 days after the first-dose of re-initiation of the study drug.

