 - On the day of the re-initiation of investigational study drug, the subject must be monitored for at least 4 hours post-dose by the first-dose administrator,

following the cardiac assessment schedule and applying the discharge criteria as described for Day 1 [see Section 5.1.10].

- If the subject missed taking the dose for up to three consecutive days during treatment maintenance (from Day 15 onwards after the first dose of initiation/re-initiation of the study drug):
 - Dosing should be resumed in the morning, with the same dose taken prior to study drug interruption.
 - Study drug intake may be re-initiated by the subject at home.
 - Subjects must be instructed to contact the investigator immediately if they experience any symptoms of bradycardia (e.g., dizziness, vertigo, syncope).
- If the subject missed taking the dose for four or more consecutive days during treatment maintenance (from Day 15 onwards after the first dose of initiation/re-initiation of the study drug):
 - The original up-titration scheme for the investigational study drug needs to be re-applied.
 - On the day of the re-initiation of treatment, the subject must be monitored for at least 4 hours post-dose by the first-dose administrator, following the cardiac assessment schedule and applying the discharge criteria as described for Day 1 [see Section 5.1.10].

Whenever the investigator / treating neurologist becomes aware that the subject did not report having missed the study drug intake for one or more days during up-titration or four or more days during maintenance and has continued dosing, the subject should be interviewed by the investigator / treating neurologist for any symptoms related to bradycardia and further examinations (e.g., 12-lead ECG, BP measurement) may be performed at the discretion of the investigator / treating neurologist. Based on an assessment of the clinical findings and the likelihood of subject's adherence to treatment, the investigator / treating neurologist will determine whether the patient can continue regular dosing, needs to re-initiate treatment, or should permanently discontinue treatment.

Figure 2 Algorithm for management of treatment

5.1.10 Criteria for discharge from cardiac monitoring on Day 1, and on the first day of re-initiation of the investigational study drug following treatment interruptions

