8.4.2 Additional unscheduled visits for re-initiation of study drug (I1, I2, etc.)

As described in detail in Section 5.1.9, subjects may need to be monitored at the study site when re-initiating study drug following a study drug treatment interruption.

In such cases, there will be two visits; one visit on the day of re-initiation (d1) and an additional visit 14 days (\pm 1 day) after the day of re-initiation (d15).

The following assessments/procedures must be done during the visit on the day of re-initiation (d1):

- Body temperature.
- 12-lead ECG pre-dose and hourly (\pm 15 minutes) for up to 12 hours post-dose (under the responsibility of the first-dose administrator).
- SBP/DBP pre-dose and hourly (\pm 15 minutes) for up to 12 hours post-dose (under the responsibility of the first-dose administrator).
- Recording of AEs and SAEs.
- IRT call and study drug dispensing.

The discharge criteria will be applied as described for Day 1. Subjects may be discharged from cardiac monitoring if they meet the discharge criteria before 12 hours post-dose but no sooner than 4 hours post-dose [see Section 5.1.10].

The following assessments need to be done during the visit 14 days after the day of re-initiation:

- Body temperature.
- SBP/DBP (pre-dose).
- 12-lead ECG (pre-dose).
- Recording of AEs and SAEs.
- IRT call – return of study drug blisters and unused medication, and dispensing of new blisters, if appropriate.

The date of visit and any data related to study assessments performed during this visit (12-lead ECGs, SBP/DBP) will be reported on the specific eCRF pages for unscheduled visit for re-initiation of study drug when post-dose monitoring is required.

These visits for the cardiac monitoring of the subjects for re-initiating study drug when post-dose monitoring is required are additional unscheduled visits. The regular scheduled study visits must be resumed according to the original visit and assessment schedule. If the visit occurs at the same time as a regular visit, all assessments of the regular visit have to be performed in addition.

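### The re-initiation rules are not reconciled on the re-titration trigger during titration, on which phase Day 15 belongs to, or on the dose resumed at the phase boundary

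*Protocol*

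**What the plan says.** - **Section 5.1.2.1 (Titration).** The two-week regimen is used on Day 1 and "on days of re-initiation of treatment following treatment interruption of more than 3 days", with a cross-reference to Section 5.1.9. The text does not distinguish titration from maintenance. It adds: "Study treatment up-titration, other than described above, is prohibited". Section 5.1.8 repeats that prohibition by reference to Section 5.1.2.1.
- **Section 5.1 and Table 4.** Titration is Days 1 to 14, with 10 mg on Days 12 to 14. Maintenance is 20 mg from Day 15. A footnote on the 10 mg row says: "Visit 4 is to take place at Day 15 ± 1 day".
- **Section 5.1.9, titration branch.** This applies when doses are missed "for one or more days during treatment up-titration (from 1 to 14 days after the first-dose of initiation/re-initiation" of study drug. The original scheme starts again, with at least 4 h of post-dose monitoring by the first-dose administrator.
- **Section 5.1.9, maintenance branch.** This applies "from Day 15 onwards after the first dose of initiation/re-initiation of the study drug". For up to three consecutive missed days: "Dosing should be resumed in the morning, with the same dose taken prior to study drug interruption". The restart may be at home. For four or more consecutive missed days, the scheme is re-applied with monitoring.
- **Section 8.4.2.** After a monitored re-initiation there is a visit on d1 and another 14 days (± 1 day) "after the day of re-initiation (d15)".
- **Section 5.1.7.2.** The diary tells the subject to contact the investigator before the next dose after one or more missed tablets in titration, or four or more missed doses in maintenance.

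**The concern.** Section 5.1.2.1 says that gradual up-titration is there to mitigate first-dose effects on heart rate and AV conduction. Whether a gap in dosing leads back to the starting dose under observation, or to resumption at home, should therefore not depend on which section a site reads or how it counts days. At three points the text can give different instructions for the same missed dose: a short gap during titration, a gap starting on Day 15, and the tablet taken when dosing resumes after such a gap. Subject safety is the main stake. A secondary one is that Section 11.1.4 lists an incorrect dose among the reasons for excluding a subject's later data from the per-protocol set, so what counts as correct needs a single answer.

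**Working it through.** The plan states no figure to reproduce. The check sets the rules side by side and converts the day windows to study days.

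**1. Trigger by phase and length of gap.** In whole days, more than 3 days is the same as 4 or more.

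| Phase | Missed days | Section 5.1.2.1 | Section 5.1.9 | Agree? |
|---|---|---|---|---|
| Titration | 1 to 3 | trigger not met | full scheme again, at least 4 h monitoring | **No** |
| Titration | 4 or more | re-titrate | full scheme again, at least 4 h monitoring | Yes |
| Maintenance | 1 to 3 | trigger not met | resume; home restart allowed | Yes |
| Maintenance | 4 or more | re-titrate | full scheme again, at least 4 h monitoring | Yes |

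One cell of four differs. The threshold in Section 5.1.2.1 is the maintenance threshold of Section 5.1.9; the one-day titration trigger is missing from it.

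**2. Phase boundary.** With the first dose on Day 1, a day that is *n* days after the first dose is Day 1 + *n*.
- Titration window in Section 5.1.9: *n* = 1 gives Day 2 and *n* = 14 gives Day 15, so Days 2 to 15.
- Maintenance window in Section 5.1.9: Day 15 onwards.
- Overlap: exactly one day, Day 15.

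Section 8.4.2 counts in the same way: 14 days after d1 is 1 + 14 = d15. For a dose missed on Day 15 alone, the titration branch restarts the scheme with at least 4 h of monitoring, while the maintenance branch resumes dosing, possibly at home. Section 5.1 and Table 4 contain no overlap.

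**3. Dose resumed at the boundary.** Take Day 15 as maintenance, and a subject whose last tablet was 10 mg on Day 14.

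| Days missed | Resumes on | Dose before the gap (Section 5.1.9) | Table 4 dose on that day |
|---|---|---|---|
| 15 | Day 16 | 10 mg | 20 mg |
| 15–16 | Day 17 | 10 mg | 20 mg |
| 15–17 | Day 18 | 10 mg | 20 mg |

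The contradiction does not depend on the overlap in step 2. It disappears once one 20 mg tablet has been taken: a subject dosed on Day 15 who then misses one to three days resumes 20 mg under both texts.

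**4. Visit window.** Day 15 ± 1 day allows Visit 4 on Day 14, 15 or 16. Study drug is dispensed at Visit 4 (Section 8.2.3). The text does not say which tablet is taken on Day 15 when the visit falls on Day 16.

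**The case against.** The strongest reply is that Section 5.1.9 is one coherent algorithm with two phase-specific branches, and that Section 5.1.2.1 is a short summary pointing to it. Much of this stands. Section 5.1.2.1 does not say that re-titration applies only after more than 3 days, gives no monitoring instruction of its own, and cross-refers to Section 5.1.9. Section 5.1.8 also names Section 5.1.9 as the place for detailed guidance. The diary alerts and the paragraph on unreported missed doses use the same one-day and four-day cut-offs. On Day 15, Section 5.1, Section 5.1.1, Table 4 and Section 8.2.1 all point to titration ending on Day 14.

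Several stronger readings are tempting but not supported:
- **Three incompatible re-titration rules.** There are two branches of one rule and one incomplete summary.
- **A conflict with the ban on other up-titration.** Section 5.1.9 re-applies the original scheme, which is not a different titration.
- **Titration tablets running out on Day 14, before a Day 16 visit.** No section says so. Section 5.1.6.3 provides enough supply to reach the next scheduled visit.
- **An unmonitored first 20 mg dose as a new hazard.** Section 8.2.3 lists only pre-dose ECG and blood pressure at Visit 4, so this step has no post-dose monitoring in the ordinary schedule either.
- **Sizing the risk from the half-life of about 32 h in Section 1.3.2.1.** The same proportional decline follows any three-day maintenance gap, for which home resumption is openly allowed, and the protocol gives no concentration threshold.
- **A definite effect on the per-protocol set.** Section 11.1.4 leaves the detailed exclusion definitions to the SAP.

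The reply leaves three things unanswered: the summary omits a trigger, the operative bullet in Section 5.1.9 still reaches Day 15 as worded, and its resumed dose still disagrees with Table 4 at the boundary.

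**Conclusion.** The point holds as a wording conflict of limited extent: one of four phase-by-gap combinations for the trigger, one study day for the phase boundary, and three gap patterns (one, two or three days missed from Day 15 after 10 mg on Day 14) for the resumed dose. Nothing in sample size, power or alpha depends on it. It still needs correcting because the text determines dose and cardiac monitoring, and sites reading it in good faith could act differently on the same missed dose.

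The conclusion rests on counting the first dose as Day 1, which the protocol does itself, and on reading the Section 5.1.9 window as worded. Figure 2, the site-facing algorithm, could not be read for this point. The amendment rationale says it was aligned with the Section 5.1.9 definition of maintenance, but that does not show how it treats Day 15 or the resumed dose. How often these situations will occur cannot be estimated from the protocol.

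**What to change.** The sponsor should reconcile Sections 5.1.2.1, 5.1.8, 5.1.9 and Table 4, then check Figure 2 and the diary alert logic (Section 5.1.7.2) against the result. Each of the following should be stated once and consistently:

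1. the re-titration trigger in each phase, with Section 5.1.2.1 either giving both or deferring wholly to Section 5.1.9;
2. the boundary between titration and maintenance, with both periods counted in the same unit so that no day falls in two branches;
3. the dose resumed after a gap that starts at the boundary, in words that cannot disagree with Table 4, including which tablet covers Day 15 when Visit 4 falls on Day 16.

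Which clinical rule applies at each point is for the sponsor's clinical team; this review does not choose one. The cost is a protocol wording change, a memo to sites and a check of the diary programming. No extra visits or subjects are needed.

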5.1.2.2 Maintenance

On the day of the study visits, study treatment must be administered only after the completion of the pre-dose safety assessments (diastolic BP [DBP], systolic BP [SBP], ECGs, PFTs, laboratory tests) and PK sampling (if scheduled).

5.1.3 Treatment assignment

A total of 600 eligible subjects will be randomized in a 1:1 ratio to ponesimod 20 mg or placebo, stratified by baseline EDSS score (EDSS ≤ 3.5, EDSS > 3.5).

Each of the study sites will be assigned a unique site number, and every subject will receive a unique screening number (= subject number), which identifies the subject throughout the study. After having confirmed the eligibility of the subject and informed consent has been signed, the investigator/delegate contacts the Interactive Response Technology system (IRT) at Visit 3 to randomize the subject. The IRT assigns a randomization number to the subject, and assigns the treatment kit number which matches the treatment arm assigned by the randomization list to the randomization number.

The randomization list is generated by an independent Contract Research Organization (CRO) and kept strictly confidential.

